3.5. Rationale

3.5.1. Rationale for Study

Enhancer of zeste homolog 2 (EZH2), a component of the Polycomb Repressor Complex 2 (PRC2), mediates transcriptional repression of target genes through tri-methylation of histone H3 on lysine 27 (H3K27me3). EZH2 and H3K27me3 are dysregulated in many cancers through diverse pathways. While EZH2 mutation plays a significant role in progression of certain lymphomas, data from prostate, breast, and several other solid tumors have demonstrated that increased EZH2 expression correlates with increased aggressiveness of tumors and poor prognosis.

GSK2816126 is a selective and potent inhibitor of wild-type and mutant EZH2 capable of decreasing H3K27me3 levels in all cell types examined. EZH2 inhibition has been shown to decrease the growth of several cell lines derived from EZH2 wild type (WT) and mutant lymphomas, SNF5-mutant malignant rhabdoid tumors, multiple myeloma, AML, neuroblastoma, prostate, breast, skin and colon cancers.

Most of these cancers have an overall poor outlook either because of lack of any effective therapy or standard therapies do not result in a durable remission. This first study of this agent will be conducted in subjects with non-Hodgkin lymphomas, especially germinal center B-cell diffuse large B-cell lymphoma (GCB-DLBCL) and transformed follicular lymphoma (t-FL), and subjects with multiple myeloma or solid tumors who have relapsed or are refractory to prior therapies and have a high degree of unmet medical need in terms of available treatment options.

3.5.2. Rationale for Population

[figure not shown]
Preclinical studies demonstrate that B-cell lymphomas of DLBCL origin with EZH2 activating mutations are the most sensitive to GSK2816126; however, the growth of a subset of EZH2 wild-type lymphomas, SNF5-mutant malignant rhabdoid tumors, multiple myeloma, AML, neuroblastoma, prostate, breast, skin, and colon cancers are also sensitive to EZH2 inhibition. There is increasing evidence that a large number of solid tumors or subtypes may be driven by EZH2 mutation or over expression. Often, these tumors have poor prognosis. Therefore, the study includes subjects with non-Hodgkin Lymphoma and enriched for subsets (GCB-DLBCL, tFL) as well as multiple myeloma and solid tumors that have relapsed or are refractory to prior treatment with standard of care or do not have standard of care available or refuse standard of care therapy.

Part 1 will be comprised of 2 phases:

- Part 1 dose escalation which will include subjects with MM, relapsed/refractory tFL and DLBCL, other NHLs and solid tumors , and
- Part 1 cohort expansion at the highest tolerated dose/MTD which will include a cohort of subjects with relapsed/refractory GCB-DLBCL and a cohort of subjects with prostate cancer or solid tumors containing EZH2 inhibitor sensitizing mutations.

Part 2 will be comprised of cohort expansions in subjects with GCB-DLBCL, transformed follicular lymphoma and multiple myeloma.

EZH2 and H3K27me3 are dysregulated in nearly all cancers through numerous pathways including 1) recurrent gain-of-function heterozygous mutations in germinal center B-cell (GCB) DLBCL, FL, melanoma, and parathyroid adenoma, 2) EZH2 over-expression in numerous other aggressive tumors including those from prostate, breast, lung, liver, bladder, head and neck, skin, and kidney, and 3) inactivating mutations in UTX. H3K27 demethylase that acts in opposition to EZH2, described in numerous tumor types including transitional cell bladder carcinoma, esophageal squamous cell carcinoma, renal cell carcinoma, multiple myeloma, and subgroup 4 medulloblastoma [McCabe, 2014]. Furthermore, data from prostate, breast, and several other tumor types have demonstrated that increased EZH2 expression correlates with increased aggressiveness of tumors and poor prognosis [GlaxoSmithKline Document Number [2013N169204_04](#), 2017]

McCabe, 2014

Table 1. Tumor types harboring EZH2-activating mutations.

Tumor type	Tumor subtype	Mutated	Total	Frequency (%)	Mutations observed	Ref.
Lymphoma	NHL	33	127	26.0	1 A677G 1 A687V 31 Y641X	[28]
		4	25	16.0	Y641X	[32]
		5	35	14.3	Y641X	[33]
		5	41	12.2	1 A677G 4 Y641X	[12]
		31	320	9.7	Y641X	[13]
	GCB DLBCL	1	73	1.4	Y641X	[34]
		18	83	21.7	Y641X	[13]
		0	42	0.0	Y641X	[13]
	ABC DLBCL	101	366	27.6	7 A677G 5 A687V 50 Y641X	[26]
		12	55	21.8	Y641X	[33]
		9	60	15.0	Y641X	[32]
		26	221	11.8	Y641X	[10]
		18	251	7.2	Y641X	[13]
	Burkitt lymphoma	0	23	0.0	Y641X	[33]

With regard to haematological indications for GSK2816126, preclinical studies demonstrate that B-cell lymphomas of DLBCL with EZH2 activating mutations are the most sensitive to GSK2816126. Approximately 22% of GCB-DLBCL tumors have an EZH2-activating mutation, whereas ABC DLBCL does not contain EZH2- activating mutations (McCabe, 2014). Early follicular lymphoma lesions have been shown to have EZH2 mutations, as well as mutations in other genes that disrupt chromatin structure [Friedberg, 2015].

Of particular interest is that there is some data to suggest that certain tumor types may respond to EZH2 inhibitors regardless of EZH2 inhibitor sensitizing status. Data presented at ASH Lymphoma Biology 2016 [Morschhauser, 2016] suggests that patients who have DLBCL (both GCB or nonGCB) and EZH2 mutated FL who are treated with the EZH2 targeted agent tazemetostat can achieve responses, providing proof of concept in DLBCL. Patients with GCB-DLBCL were analysed by EZH2-mutation status. Of patients with EZH2 mutation 1/5 had a PR [Overall Response Rate (ORR)=20%]. Of those without a mutation, 3/19 had PR or CR (ORR=15.7%; 2 with CR). Therefore, Part 1 cohort expansion in GCB-DLBCL will enroll patients regardless of EZH2 related mutation status.

Neuroendocrine prostate cancer (NEPC) is a subtype of castration-resistant prostate cancer associated with aggressive clinical features and poor overall survival (Wang, 2014). Mounting evidence suggests that NEPC evolves from prostate adenocarcinoma as one mechanism of resistance to androgen. Data from metastatic biopsies obtained from patients progressing on abiraterone or enzalutamide suggests that at least 10% of patients with late-stage castration-resistant prostate adenocarcinoma (CRPC) eventually develop small-cell NEPC. NEPC cancer is driven by N-Myc. N-Myc in turn drives EZH2, making neuroendocrine prostate cancer sensitive to inhibition [Dardenne, 2016]. Additionally,

EZH2 has been described as an epigenetic driver of aggressive prostate cancer. EZH2 dysregulation may be involved in the progression from early prostate cancer to late [Yang, 2013]. One of the most prevalent genetic modifications observed in prostate cancer is the fusion between the TMPRSS2 and ERG genes, resulted from an abnormal translocation on chromosome 21. Detected in more than half of all prostate tumors, this fusion gene consisting of the androgen-responsive TMPRSS2 promoter and the ERG coding region is able to substantially upregulate ERG expression, which has been proven to induce cell proliferation and invasion [Kumar-Sinha, 2008]. Notably, it has been demonstrated that ERG can directly activate EZH2, which synergistically result in cancer progression through histone methylation linked de-differentiation [Yu, 2010]. Several studies have also confirmed that expression of EZH2 shows a correlated pattern with the stage of prostate cancer development [Berezovska, 2006; Saramaki, 2006; Hoffmann, 2007]. Therefore, subjects with prostate cancer will be enrolled regardless of EZH2 related mutation status.

This study of GSK2816126 will focus primarily on the GCB-DLBCL NHL in order to ascertain a clinical benefit in a defined tumor type, for which there is high probability of potential benefit. However, solid tumors with changes to EZH2 inhibitor sensitizing mutations will be evaluated. These will be targeted as it is felt that they are most likely to show benefit. The exception in the solid tumor cohort will be prostate cancer, for which no mutation status will be required.

3.5.3. Rationale for Dose and Schedule

The doses of GSK2816126 for evaluation in this study were selected based on available preclinical biology, toxicology, and pharmacokinetic data as well as predicted pharmacokinetic and response information for humans. Refer to the IB for more information [GlaxoSmithKline Document Number [2013N169204_04](#), 2017].

Human Pharmacokinetic Extrapolation

Whole blood human clearance was predicted from three species (mouse, rat and dog) using maximum life span power-law allometry to be around 8.2 ml/min/kg. Volume of distribution was predicted from simple power-law allometry to be 4.8 L/kg and half-life around 6.5 hours. A 70 kg adult therefore has a predicted total clearance of 35 L/hr and a total volume of distribution of 336 L.

Starting Dose and Infusion Duration

Three approaches have been considered to establish the starting dose for GSK2816126 in hematological malignancies assuming a 70 kg adult with a surface area of 1.7 m².

- One tenth of the rat STD10 as per ICH S9 guidance

The STD10 in the rat was defined as 100 mg/kg administered over 6-hour infusion twice-weekly for 2 to 4 weeks. One-tenth (1/10) of the rat STD10 is 60 mg/m².

These doses were well tolerated in dogs. A starting dose based on 1/10 of the rat STD10 would be 110 mg using the human equivalent dose calculation.

- One sixth of the dog HNSTD as per ICH S9 guidance

Based on tolerability, the HNSTD in the dog was defined as 100 mg/kg administered as an 8-hour infusion twice-weekly for 4 weeks. A starting dose based on 1/6 of the dog HNSTD would be 610 mg using the human equivalent dose calculation.

- The minimum anticipated biologically effective dose

A daily dose of 15 mg/kg or twice-weekly dose of 50 mg/kg in the Pfeiffer xenograft mouse model resulted in minimum target engagement as measured by a 15% reduction in H3K27 tri-methylation and 35% to 38% tumor growth inhibition. The minimum anticipated biologically effective dose is 287 mg twice-weekly based on providing similar free exposure while the dose would be 800 mg based on providing similar total blood exposure.

An infusion duration of 2-hours is proposed for this clinical study. This infusion duration is shorter than the infusion duration used in animals but can be justified based on the following points:

- With infusion of a volume of 250 mL over 2 hours, GSK2816126 doses up to 1250 mg will provide infusion concentration up to the infusion concentration of 5 mg/mL used in dogs while doses up to 2500 mg will provide infusion concentration up to the concentration of 10 mg/mL used in rats. A 3000 mg dose would provide an infusion concentration of 12 mg/mL.
- The infusion will be performed into a larger (central) vein in humans than in animals. A shorter infusion duration and higher local blood flow would lead to a shorter exposure of the local area of the vein to high concentrations of GSK2816126.
- The main factor for the long infusion duration in animals was the histamine-release like reaction. Subjects will be monitored during the infusion for evidence of histamine release related symptoms/infusion reactions and treated as needed with supportive care per local standard of care (e.g., corticosteroids, oxygen, epinephrine, diuretics, IV fluid). The infusion duration can be lengthened with restart of the infusion or at the next infusion. Premedications (antihistamines or similar) may be provided at the next infusion or prior to treatment of new subjects.

Taking all three approaches into consideration and the shorter infusion duration of 2-hours, a starting dose of 50 mg twice-weekly as a 2-hour infusion is proposed. This dose provides a predicted total blood AUC of 1.43 μ g.h/mL and a total blood Cmax of 0.428 μ g/mL. The AUC is 38-fold lower than the AUC (0-24hr) for the rat STD10 of 100 mg/kg, 18-fold lower than the AUC at the lowest tested dose in rat (30 mg/kg), and 56-fold lower than the AUC for the dog HNSTD of 100 mg/kg. The Cmax is 18-fold lower than the Cmax for the rat STD10 of 100mg/kg, 6.9-fold lower than the Cmax at the lowest tested dose in rat (30 mg/kg), and 23-fold lower than the Cmax for the dog HNSTD of 100 mg/kg. The starting dose of 50 mg will provide a suitable safety margin for the anticipated toxicities, while minimizing the number of subjects with aggressive lymphomas exposed to sub-therapeutic doses.

Predicted Effective Dose and Dosing Frequency

The potential therapeutic dose for GSK2816126 in human was derived using available preclinical, PK and efficacy data from Karpas-422 and Pfeiffer tumor xenograft studies. Based on PK/PD modeling of Karpas-422 and Pfeiffer xenograft data, tumor eradication with GSK2816126 could be achieved in mice with an average total blood concentration target over the dosing interval of 1 ug/mL or an average free concentration of 16ng/mL. This free concentration is similar to the in vitro exposure producing 50% of the maximum effect (EC₅₀) obtained in Karpas-422 or Pfeiffer cell lines and to the average free concentration obtained with 50 mg/kg dosed daily in Karpas-422 xenograft model where more than 90% tumor growth inhibition was observed. This average free concentration could be achieved on average with twice-weekly administration of 950 mg in humans. Due to species differences in protein binding and blood to plasma partitioning, a dose of up to 2700 mg could be needed to achieve the average total blood concentration target of 1 ug/mL.

The rationale for the proposed schedule of twice weekly, 3 weeks on / 1 week off for each 28-day cycle is based on preclinical *in vivo* observations. Briefly, mice with Pfeiffer tumor xenograft were treated daily with 50 mg/kg for 10 days. Tumor H3K27 trimethylation levels were measured and tri-methylation inhibition was observed up to 5 days after the last administration. Using *in vivo* murine tumor xenograft models, schedules with progressively longer dosing intervals (i.e., from daily to once or twice-weekly to intermittent twice-weekly dosing with 2 weeks on/ 1 week off) were evaluated. Similar tumor growth inhibition were observed for the same total weekly dose, regardless of dosing frequency, except for lower tumor growth inhibition being observed with once weekly dosing.

Taken together, these data support a schedule of twice weekly, 3 weeks on / 1 week off.

3.6. Study Treatment

3.6.1. Treatment Assignment

- This is an open-label study
- Subjects will be identified by a unique subject number that will remain consistent for the duration of the study

3.7. Dosage and Administration of Study Treatment

Due to the risk of infusion site reaction and/or infusion rate/concentration dependent histamine reactions, central venous access such as a port, Hickmann catheter or PICC line will be required.

GSK2816126 will be administered initially twice-weekly 3 weeks on / 1 week off of each 28-day cycle. The dose of the study treatment is discussed in Section 3.3 and Section 3.4.

Investigational product (IP) details are provided in [Table 5](#). It will be diluted in saline or D5W to a fixed 250 mL volume. This volume will be infused over a minimum of 2 hours (up to 4 hours). Additional details are provided in the SPM.

3.8. Safety Management Guidelines

3.8.1. QTcF Stopping Criteria

The QTcF is the QT interval corrected for heart rate according Fridericia's formula (QTcF).

- For eligibility and withdrawal, subjects QTcF value will be used.
- For purposes of data analysis, QTcF values will be used.

If a subject that meets the corrected QTcF¹ interval duration criteria below, study treatment(s) will be withheld.

- QTcF interval \geq 500 msec; GSK2816126 will be permanently discontinued.
- QTcF interval increase from baseline \geq 60 msec and maximum QTcF $<$ 500 msec; GSK2816126 may be restarted one dose level lower once the QTcF returns to baseline. If QTcF prolongation meeting stopping criteria recurs after re-challenge, GSK2816126 must be permanently discontinued.

¹Based on average QTcF value of triplicate electrocardiograms (ECGs) to include manual over-read. For example, if an ECG demonstrates a prolonged QTcF interval, obtain 2 additional ECGs over a brief period (e.g., within approximately 10 minutes of the abnormal ECG, if possible, and approximately 10 minutes apart from each other), and then use the averaged QTcF values of the 3 ECGs to determine whether the subjects should have study treatment discontinued.

3.8.2. Infusion Reaction Stopping Criteria and Management

A subject may be withdrawn from treatment with GSK2816126 for safety-related reasons if the following criteria are met:

- Occurrence of a \geq Grade 3 infusion-related reaction that does not resolve to \leq Grade 1despite adequate clinical intervention and prevents re-initiation of the infusion on any given treatment day

3.8.2.1. Management of Infusion Reactions

Infusion Related Reaction

Infusion Related Reaction	
Grade 1: Continue infusion and closely monitor the subject
 
Grade 2/3: Temporarily interrupt study medication and:
 
 - Administer diphenhydramine or similar anti-histamine - Provide supportive care per local standard of care (e.g., corticosteroids, oxygen, epinephrine, diuretics, IV fluid) - May resume infusion once resolved to \leqgrade 1* - For grade 3 reactions, corticosteroids may be considered 
Grade 4:
 
 - Discontinue infusion. Administer diphenhydramine, corticosteroids and supportive care per local standard of care - May consider restarting study treatment at a reduced dose or dose level pre-event based on discussion with GSK Medical Monitor
---------------------------	--

*Recommend following institutional guidelines for re-starting after infusion reactions seen with cytotoxic therapy. A general guideline would be as follows:

- Restart under observation at an infusion rate of 25% of the original rate for the first 30 minutes
 - If no reaction, increase infusion rate by 25% of the original rate every half hour until full dose administered
 - If Grade 1 reaction, continue at the rate at which the reaction occurs
- If Grade 2 or 3 infusion related reaction consider premedication for all subsequent infusions per local standard of care.

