Infusion rate and/or concentration-dependent, histamine reactions, which began within minutes of dose initiation, were observed at ≥ 300 mg/kg in dogs (C_{max} 66.5 to 130 μ g/mL) and 300 mg/kg (C_{max} 33.9 to 54.2 μ g/mL) in rats. In dogs, histamine reactions resulted in discontinuation of dosing. Histamine-related decreased body temperature, along with increased heart rate (HR) and decreased blood pressure (BP) likely led to mortality in restrained, but not in unrestrained, rats given an IV infusion of 300 mg/kg (5 mL/kg/hr for 4 hours). These effects could be ameliorated by discontinuation of dosing, administration of diphenhydramine hydrochloride, degranulation of mast cells prior to GSK2816126 dosing, and/or lengthening of the infusion time to reduce C_{max} . These observations tended to occur only during the first exposure to the drug and not on subsequent administrations. Human subjects will be monitored during the infusion for evidence of histamine release related symptoms/infusion reactions and treated as needed with supportive care per local standard of care. (e.g., corticosteroids, oxygen, epinephrine, diuretics, IV fluid). The infusion duration can be lengthened with restart of the infusion or at the next infusion.

Premedications (antihistamines or similar) may be provided at the next infusion or prior to treatment of new subjects.

In dogs, a mild, reversible dose dependent decrease in minute (up to 128 mL/min/kg; 49%) and tidal volume (8 mL/kg; 56%) at 100 mg/kg and an elevation in Corrected QT interval duration (QTc) interval at 30 (maximum increase of 12 msec or 5%) and 100 (maximum increase of 18 msec or 8%) mg/kg were observed following the end of a single 8 hour infusion. These effects did not directly correlate with peak GSK2816126 blood levels as the onset was 4-7 hours following the end of the infusion. QTc interval elevations were not observed following repeat dosing.

A direct effect on human ether à go-go-related gene (hERG) channel repolarization is unlikely (IC_{25} of 54.2 μ M; 28.61 μ g/mL), however, GSK2816126 did block hERG current density in vitro consistent with an effect on hERG channel trafficking. The mechanism for this change is unclear. Evaluation of the QTc interval has been incorporated into this clinical study protocol.

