3.3.3. Dose Limiting Toxicity

Dose-limiting toxicity (DLT): An event will be considered a DLT if it occurs within the first 4 weeks (28 days) of treatment and meets one of the following criteria (Table 3 [NCI-CTCAE, 2009]) unless it can be clearly established that the event is unrelated to treatment.

Table 3 Dose-Limiting Toxicity Criteria

Toxicity	DLT Definition
Hematologic	
 Grade 4 absolute neutrophil count (ANC) for >7 days Febrile neutropenia (according to CTCAE v.4.0 criteria) Grade 4 thrombocytopenia or anemia for >7 days
Non-hematologic	
 Grade 3 or greater nausea, vomiting, or diarrhea that does not respond to standard medical care within 48 hours Grade 3 or greater clinically significant non-hematologic toxicity per national cancer institute - common terminology criteria for adverse events (NCI-CTCAE), v 4.0
Infusion reactions	
 Infusion reactions will not be considered a DLT unless a \geqgrade 3 reaction recurs after administration of optimal prophylaxis
Other	
 Inability to receive >75% of scheduled doses in treatment period due to toxicity Grade 2 or higher toxicity that does not meet the above definitions but, in the judgment of the investigator and GSK medical monitor, is dose limiting Grade 2 or higher toxicity which occurs beyond 28 days which in the judgment of the investigator and GSK Medical Monitor is considered to be a DLT

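### The fallback infusion-restart scheme in Section 3.8.2.1 states no maximum rate, so read literally it steps above the original rate after an early reaction

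*Protocol*

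**What the plan says.** Section 3.8.2.1 interrupts the infusion for a Grade 2 or 3 reaction, calls for an antihistamine and supportive care, and allows a restart once the reaction is Grade 1 or less. On how to restart, local rules come first: "Recommend following institutional guidelines for re-starting after infusion reactions seen with cytotoxic therapy". A general guideline then follows. Its first step is "Restart under observation at an infusion rate of 25% of the original rate for the first 30 minutes". Its second is "If no reaction, increase infusion rate by 25% of the original rate every half hour until full dose administered". A Grade 1 reaction during the restart holds the rate where it is. No other limit on the rate appears there.

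Section 3.7 fixes the volume at 250 mL and adds: "This volume will be infused over a minimum of 2 hours (up to 4 hours"). Table 5 repeats the 2 to 4 hours. Section 3.7 also requires central venous access, partly because of "infusion rate/concentration dependent histamine reactions". Section 1.2.2 reports from rats and dogs: "Infusion rate and/or concentration-dependent, histamine reactions, which began within minutes of dose initiation". On managing such reactions, Section 3.5.3 says: "The infusion duration can be lengthened with restart of the infusion or at the next infusion".

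**The concern.** A step-up scheme that ends on dose rather than on rate keeps climbing for as long as drug remains in the bag. The earlier the reaction, the more drug remains and the higher the steps go. The protocol describes the histamine reactions as related to infusion rate and/or concentration, and in animals they came early. So the subjects for whom the literal wording climbs highest are those whose reaction fits the pattern the protocol describes. With the volume fixed, the bag concentration at a given dose cannot be lowered, which leaves rate as the adjustable quantity. A site that follows the guideline to the letter would end such an infusion faster than it began.

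**Working it through.** The protocol gives no peak restart rate, so there is no stated figure to reproduce.

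**Inputs.** Volume 250 mL and planned length T of 2 to 4 h (Section 3.7); the 3-h case also appears in Table 7. Restart at 25% of the original rate, adding 25% each half hour (Section 3.8.2.1). Let t0 be the running time at which the infusion was stopped. Pauses are ignored and no further reaction occurs.

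**Steps.** Measure drug in hours at the original rate, so the bag holds T and T − t0 is left at restart. Step k runs at 0.25k of the original rate for 0.5 h and delivers 0.125k.

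| Step | Rate | Delivered | Cumulative |
|---|---|---|---|
| 1 | 25% | 0.125 | 0.125 |
| 2 | 50% | 0.250 | 0.375 |
| 3 | 75% | 0.375 | 0.750 |
| 4 | 100% | 0.500 | 1.250 |
| 5 | 125% | 0.625 | 1.875 |
| 6 | 150% | 0.750 | 2.625 |
| 7 | 175% | 0.875 | 3.500 |

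The rate passes 100% when T − t0 > 1.25. It reaches 150% when T − t0 > 1.875, 175% when T − t0 > 2.625, and 200% when T − t0 > 3.5. The top step is longest as t0 approaches 0.

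| Planned T | Original rate | Above 100% if t0 is before | Highest step | Reached if t0 is before | Longest time in that step |
|---|---|---|---|---|---|
| 2 h | 125 mL/h | 45 min | 150% = 187.5 mL/h | 7.5 min | 0.125/1.5 h = 5 min |
| 3 h | 83.3 mL/h | 1 h 45 min | 175% = 145.8 mL/h | 22.5 min | 0.375/1.75 h = 13 min |
| 4 h | 62.5 mL/h | 2 h 45 min | 200% = 125 mL/h | 30 min | 0.5/2 h = 15 min |

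**Typical 2-h case.** For t0 from 7.5 to 45 min the peak is 125%, or 156 mL/h. At t0 = 10 min, 1.833 is left, so 1.833 − 1.25 = 0.583 runs above the original rate. That is 0.583 × 125 = 73 mL, 29% of the bag, over 0.583/1.25 = 0.467 h = 28 min.

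**Does the 2-h minimum act as a cap?** Not as a total time. As t0 approaches 0, the uncapped 2-h infusion takes 2.5 + 0.125/1.5 = 2.58 h. For t0 between 7.5 and 45 min it takes t0 + 2 + (0.75 − t0)/1.25 = 2.6 + 0.2·t0 hours, or 2.625 to 2.75 h. Every ramp that passes 100% therefore satisfies the minimum.

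**With a cap at 100%.** Four steps take 2 h and deliver 1.25; the rest runs at 100%. Total running time is t0 + 2 + (T − t0 − 1.25) = T + 0.75 h: 2.75 h for a planned 2 h and 4.75 h for a planned 4 h.

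**The case against.** The strongest reply is that this is a literal reading of advisory text. Institutional rules come first, the scheme is only a general guideline, and Section 3.7 leaves further administration details to the Study Procedures Manual, which is not at hand. Most clinicians would stop at the original rate unprompted. All of that stands and limits the point to sites with no rule of their own.

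The ramp also has its own safeguards. Each step requires that no reaction has occurred. Passing 100% takes half an hour each at 25, 50, 75 and 100%: two quiet hours under observation, after an antihistamine, including 30 minutes at the original rate. Section 1.2.2 adds that in animals diphenhydramine could ameliorate the reactions and that they tended to occur only on first exposure. This stands too, and it makes harm less likely without supplying the missing ceiling.

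The 2-hour minimum for a fixed 250 mL could be read as a rate limit of 125 mL/h. That would exclude the overshoot on a 2-h infusion. The text states a duration, however, and a 125 mL/h limit would still allow a 4-h infusion to double its rate.

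Two larger consequences might be inferred. Neither is supported.

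- **Dose-limiting toxicity.** One might say that a recurrence during the ramp would count against the dose level. Section 3.3.3 counts an infusion reaction only if a Grade 3 or higher "reaction recurs after administration of optimal prophylaxis". Section 3.8.2.1 places premedication at subsequent infusions; the antihistamine given during the interruption is treatment. In a premedicated subject with a previous Grade 3 reaction, another Grade 3 reaction that stops the infusion would already meet the definition before any ramp. The remaining route is narrow, and the protocol gives no frequency for it.
- **Undoing a lengthened infusion.** A planned 4-h infusion stopped at 10 minutes would take 0.167 + 3.5 + 0.333/2 = 3.83 h of running time uncapped. That is slightly under 4 h but nearly twice 2 h, and any pause over 10 minutes takes the elapsed time past 4 h.

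**Conclusion.** The wording is defective, but the defect is small. Followed literally, the guideline ends above the original rate on a 2-h infusion stopped before 45 minutes and on a 4-h infusion stopped before 2 h 45 min. The usual overshoot on a 2-h infusion is to 125%. The 150% step needs a reaction in the first 7.5 minutes and lasts at most 5 minutes. The 200% step on a 4-h infusion exceeds that subject's own original rate, but not the fastest planned rate.

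This rests on a site using the guideline as written, on no further reaction during the ramp, and on running time without the pause. A cap was probably intended. The protocol gives no event frequency and does not show that the faster rate would cause harm. Sample size, alpha, power and the dose-escalation rules are untouched. It is worth correcting because a first-in-human safety instruction should not rely on readers to supply its ceiling.

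**What to change.** In the second step of the Section 3.8.2.1 guideline, insert *not above the original rate* after the half-hourly increase and before the words on completing the dose.

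In Section 3.7 and Table 5, add: *The 2 to 4 hours are the planned, uninterrupted duration; a restarted infusion follows Section 3.8.2.1.* This is needed because a capped, restarted 4-h infusion takes up to 4.75 h of running time and should not be sped up to finish by 4 h.

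The cap still brings the subject back to the original rate, as the scheme evidently intends; slower restarts remain available under Section 3.5.3. The cost is one clause and one repeated sentence at the next amendment, with no change to doses, samples or analyses.
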